2.5.1.2 Analysis Methods

Serum ALP levels, change from baseline, and percent change from baseline will be summarized at each analysis window (see Table 2) using descriptive statistics and 95% confidence intervals. A t-test will also be performed to test for the percent change from baseline to Week 12. This analysis will be based on observed data without imputation. This analysis will be summarized within the ITT and PP population.

2.5.2 Secondary Analyses

Secondary endpoints, including the secondary ALP endpoints, will be summarized with descriptive statistics by timepoint. These summary measures will include baseline, result at the time point that data is captured, change from baseline, and percent change from baseline as is appropriate for the endpoint. A 95% confidence interval will be produced for changes in laboratory endpoints, within the ITT population.

Endpoints with categorical interpretations (e.g. ELF, GLOBE Score, Pruritus VAS) will additionally be summarized by shift tables for Change from Baseline to Week 12 using the categories listed above.

2.5.3 Subgroups

The results, change from baseline, and percent change from baseline to week 12 for ALP, total bilirubin, GGT, ALT, AST, and ELF will be performed for the following subgroups:

- ALP at Baseline (above and below median value)
- Total bilirubin at Baseline (above and below median value)

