### 4.2. Scientific Rationale for Study Design

This is a single arm, open-label proof-of-concept study. All subjects will receive active study drug treatment. This study design is appropriate for a proof-of-concept study for an intervention in a new indication for PBC patients where the laboratory markers do not improve spontaneously and over time, are expected to get worse. Hence, seeing improvements, even without a control arm, is sufficient to meet the scientific goal of providing an indication of efficacy while also providing safety data.

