2.3.1 Alkaline Phosphatase

ALP results are provided by the central and local laboratory with units of Units per Liter (U/L). Baseline is defined as the last available ALP result prior to treatment with change from baseline and percent change from baseline based upon this baseline value as the respective timepoint. Normalized ALP is defined as having ALP within the normal range (37 U/L to 116 U/L). Historical ALP will be summarized in the baseline characteristics table but not used otherwise.

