2.4.1 Definition of Baseline

Unless specified elsewhere, baseline is defined as the last available measurement prior to administration of study drug. For events that occur on the same day as the first administration of study drug (i.e. assessments performed at the Baseline visit), and for which the time of the assessment is not available, the assessment will be classified as pre-treatment, hence baseline. The exception to this rule will be AEs for which the event will be classified as a TEAE.

It should be noted that for the purpose of clinical management, the description of baseline varies in the protocol (e.g. inclusion/exclusion and Drug-Induced Liver Injury Monitoring). For analysis purposes, only the definition above will be used.

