2.5 Statistical Assessment of the Study Objectives

The efficacy endpoints will be summarized within the ITT population using descriptive statistics, with the primary endpoint, GGT and total bilirubin, also summarized within the PP

HighTide Biopharma Pty. Ltd.
Protocol HTD1801.PCT013

population. As this study includes one treatment group, the hypotheses, tests, and confidence intervals are all one sample comparisons to baseline. Confidence intervals will be 95% two-sided normal approximation confidence intervals. Testing for the percent change from Baseline to Week 12 in ALP using a t-test will also be performed. Testing will be one sided using a 5% alpha level. No multiplicity adjustment will be used, and the p-values reported for the endpoints will be descriptive in nature.

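### SAP 2.5.3 splits ALP and bilirubin change at the median of the same pre-dose value from which change is computed, so without a control arm two descriptive subgroup tables will show a false high-versus-low gradient

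*SAP*

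**What the plan says.** SAP 2.5.3 names two subgroup variables: "ALP at Baseline (above and below median value" and "Total bilirubin at Baseline (above and below median value". Results, change and percent change "for ALP, total bilirubin, GGT, ALT, AST, and ELF will be performed for the following subgroups".

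In SAP 2.4.1, "baseline is defined as the last available measurement prior to administration of study drug". SAP 2.3.1 applies this to ALP, with "percent change from baseline based upon this baseline value". For a subject who attends as scheduled, this is the Day 0 draw.

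There is no comparator. SAP 2.5 states: "As this study includes one treatment group, the hypotheses, tests, and confidence intervals are all one sample comparisons to baseline". Protocol 4.2 defends the absence of a control on the ground that "the laboratory markers do not improve spontaneously and over time, are expected to get worse".

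Neither document mentions regression to the mean, offers another variable for the split, or attaches a caution to the subgroup tables.

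**The concern.** A measured baseline is a subject's usual level plus that day's fluctuation. Sorting subjects on it puts those who happened to read high into the upper half and those who happened to read low into the lower half. At Week 12 the fluctuation is drawn afresh, so on average the upper half falls and the lower half rises with no treatment effect. A concurrent control would show the same pattern and allow it to be subtracted. Here nothing does.

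The artefact always points the same way: the drug appears to work better in subjects with higher ALP or higher bilirubin. A reader planning the placebo-controlled study mentioned in Protocol 12.4.7 and SAP 2.8 could take that for effect modification. The argument of Protocol 4.2, made for the enrolled population, cannot be carried over to a half chosen for its high reading.

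**Working it through.** **Figures in the plan.** The plan gives none for the subgroups. Its one related figure, power of at least 90% with 30 subjects, a 15% mean reduction, SD 25% and one-sided 5%, reproduces: the exact one-sample t-test gives 94.1%. This point does not touch that figure.

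**Inputs from the documents.**
- 30 subjects, so 15 per half; planned reduction 15% (SAP 1.5).
- Historical and Screening ALP both at least 1.5 x ULN, and Screening not more than 30% below historical (Protocol 5.1, criterion 4).
- Bilirubin excluded above 1.3 mg/dL apart from Gilbert's Syndrome (Protocol 5.2, criterion 7).

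**Assumptions, not in the documents.** Lognormal values; between-subject log SD 0.35 before selection; median ALP 2.0 x ULN and median bilirubin 0.6 mg/dL before selection; within-subject CV 5-15% for ALP and 20-25% for bilirubin; errors independent between visits. Gilbert's Syndrome is not modelled.

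**Hand check, ignoring selection.** Let sw and sb be the within- and between-subject SDs on the log scale. A median split on the baseline value gives an expected high-minus-low gap in log change of

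gap = -2 x 0.798 x sw² / √(sw² + sb²).

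With sb = 0.35:
- sw 0.05: 1.596 x 0.0025 / 0.3536 = 0.011, about 1 point
- sw 0.10: 1.596 x 0.0100 / 0.3640 = 0.044, about 4 points
- sw 0.15: 1.596 x 0.0225 / 0.3808 = 0.094, about 9 points
- sw 0.20: 1.596 x 0.0400 / 0.4031 = 0.158, about 16 points
- sw 0.25: 1.596 x 0.0625 / 0.4301 = 0.232, about 23 points

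For ALP, the entry threshold narrows the true spread and so widens the gap somewhat.

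**Simulation with the selection rules and no drug effect.** Mean percent change at Week 12, split as planned:

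| Analyte | CV | High half | Low half | Gap (points) |
|---|---|---|---|---|
| ALP | 8% | -1.2 | +2.4 | 3.6 |
| ALP | 10% | -1.7 | +3.7 | 5.4 |
| ALP | 15% | -3.5 | +8.0 | 11.5 |
| Bilirubin | 20% | -4.3 | +12.0 | 16.3 |
| Bilirubin | 25% | -5.8 | +18.1 | 23.9 |

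At CV 5% the ALP gap is about 1.4 points.

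**Sensitivity to the assumed spread.** With between-subject log SD 0.25-0.40 and median ALP 2.3 x ULN, the null ALP gap is 1.1-1.6 points at log SD 0.05 within subjects and 10.2-13.3 at 0.15. If the whole planned SD of 25% were within-subject noise (0.25/√2 = 0.177), it would be 13.6-17.7. That is a ceiling, not an expectation.

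**Simulation with a uniform true 15% reduction in ALP.** High/low halves: -16.0/-13.0 at CV 8% (gap 3.0), -16.5/-11.9 at 10% (4.6), -18.1/-7.9 at 15% (10.2). At CV 5% the gap is about 0.85 x 1.4 = 1.2 points. Both halves improve; only the contrast is false.

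**Splitting on Screening instead, change still from the last pre-dose value.** With independent errors the gap is about zero. If Screening and Day 0 errors correlate at r, the covariance of log change with the splitting value goes from -sw² to -r x sw². To a first approximation a fraction r of the gap therefore remains. Simulated at r = 0.3, the remainder is 1.1-2.4 of 3.5-11.0 points for ALP (22-31%) and 4.3-6.7 of 15.6-23.5 for bilirubin (28-29%). At r = 0.5 it is 2.2 of about 5 points for ALP at CV 10% (44%) and 11.5 of about 24 for bilirubin at CV 25% (48%). Across all settings tried with r between 0.3 and 0.5 the remainder was roughly 20-60%.

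**The case against.** The strongest reply is that little hangs on these tables. The SAP plans no subgroup test, interaction test or subgroup claim. The one planned test is the overall ALP t-test, and p-values are called descriptive. The interim summary in SAP 2.8 covers the primary endpoint, the other ALP endpoints and adverse events, not subgroups. All of that stands. It limits the importance of the point but does not remove it, because the bias is in the subgroup means themselves.

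Four stronger readings are tempting, and the documents do not support them.
- **That the primary result is biased.** Eligibility rests on the historical and Screening ALP, not on Day 0. In the null simulations the overall mean percent change was slightly above zero, which is against the drug.
- **That all the subgroup output is distorted.** Six analytes by two splits make twelve tables. Two are affected directly. The other ten are affected only if visit-to-visit errors correlate across analytes, which the documents do not show.
- **That the low half will appear to worsen.** This holds for little or no drug effect. At the planned effect the low ALP half improves, only less.
- **That these are the only planned groupings.** They are the only ones in SAP 2.5.3. SAP 3.3.3 also groups ALP change by UDCA dose ratio, and SAP 2.3.7 splits pruritus VAS change by baseline VAS. The VAS split has the same structure as the two at issue.

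It is also fair to say that Screening is no perfect remedy. Protocol 8.2 lets the full 28-day window be shortened, so the two draws may lie only days apart and share part of their error.

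**Conclusion.** The point holds for two descriptive tables: ALP by baseline-ALP half and bilirubin by baseline-bilirubin half. The direction is certain given any within-subject variation and no control. The size is not, because neither document reports within-subject variability. On the stated assumptions the false gap with no drug effect is about 1-12 points for ALP (CV 5-15%) and 16-24 points for bilirubin (CV 20-25%). Under a uniform 15% reduction the ALP gap is about 1-10 points. This is a minor point of interpretation with a cheap remedy. It gives no reason to doubt the primary analysis or the planned decision to proceed.

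**What to change.** In SAP 2.5.3:
1. Define both subgroups by the median of the Screening central-laboratory value. Where a test was repeated or the subject rescreened, use the value on which eligibility was decided.
2. Keep the last pre-dose value as the baseline for change and percent change.
3. Leave out of the two affected tables any subject whose baseline is itself the Screening value, since for that subject the two roles coincide again.
4. Footnote the tables to say that differences between halves may reflect regression to the mean. Put the same note on the pruritus VAS split in SAP 2.3.7.

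The cost is a short wording change. No new data are needed, since the serum chemistry panel at Screening already contains both analytes. The drawbacks are a less conventional split, a few subjects near the median changing half, and the remaining gap noted above if Screening and Day 0 errors correlate. That remaining gap is why the footnote is needed as well as the change of splitting variable.

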2.6 Handling of Missing Data

Summary statistics will generally be reported based upon observed data. Missing data will not be imputed for the efficacy analyses. Percentages will be reported for subjects with data. Missing dates for AEs and concomitant medications will be imputed to allow these items to be summarized as pre-treatment or not. Should a determination of treatment period (on treatment or pre-treatment) be required for AEs or concomitant medication, but the corresponding date is missing or partial, the event/medication will be considered on treatment unless the portions of the date that are available indicate this is not possible.

2.7 Safety Analyses

Safety endpoints will be summarized with descriptive statistics. All safety summaries and analyses will be performed using the ITT population.

Prior and concomitant medications and procedures will be coded by the World Health Organization (WHO) Drug Dictionary version Sept2020. Medications and procedures will be considered concomitant unless they ended prior to treatment.

2.8 Interim Analyses

Data will be summarized at study completion, as well as when 15 subjects have reached Week 12. At the interim timepoint, the data will be summarized descriptively: primary efficacy endpoint, additional ALP secondary endpoints, and TEAEs. For the interim analysis, only subjects with completed data who reached Week 12 will be used for efficacy analyses, all available data will be used for safety analyses.

Enrollment into the study may be stopped early prior to enrollment of all 30 subjects should the scientific goal (evaluate the effects of HTD1801 on serum ALP) of the study be achieved with the currently available data. That is, if prior to enrollment of 30 subjects, the results provide sufficient preliminary evidence of efficacy that warrant further evaluation in a placebo-controlled study, enrollment in this study may be terminated.

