#### **4.4. End of Study Definition**

A participant is considered to have completed the study if he or she has completed all phases of the study including the last visit or the last scheduled procedure shown in the Schedule of Activities, Section 1.3.

The end of the study is defined as the date of completion of the last visit or procedure shown in the Schedule of Activities in the trial globally for the last subject in the study.

The end of enrollment if less than 30 subjects will be a collaborative decision between regulatory and Sponsor entities.

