#### **12.4.7. Planned Interim Analyses**

Enrollment into the study may be stopped early prior to enrollment of 30 subjects should the scientific goal (evaluate the effects of HTD1801 on serum ALP) of the study be achieved with the currently available data. That is, if prior to enrollment of 30 subjects if the results are robust enough to provide preliminary evidence of efficacy that warrant further evaluation in a placebo-controlled study, enrollment in this study may be terminated.

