### **13.2. Study Discontinuation and Closure**

This study may be temporarily suspended or prematurely terminated if there is sufficient reasonable cause. Written notification, documenting the reason for study suspension or termination, will be provided by the suspending or terminating party to the investigators and regulatory authorities. If the study is prematurely terminated or suspended, the Principal Investigator will promptly inform study participants, the Institutional Review Board (IRB), and sponsor and will provide the reason(s) for the termination or suspension. Study participants will be contacted, as applicable, and be informed of changes to study visit schedule.

Circumstances that may warrant termination or suspension include, but are not limited to:

- Determination of unexpected, significant, or unacceptable risk to participants
- Demonstration of efficacy that would warrant stopping
- Insufficient compliance to protocol requirements
- Data that are not sufficiently complete and/or evaluable
- Determination that the primary endpoint has been met
- Determination of futility

Study may resume once concerns about safety, protocol compliance, and data quality are addressed, and satisfy the sponsor, IRB and/or Food and Drug Administration (FDA).

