1.5 Decision Rule and Sample Size

The significance level for this study is 5% (one-sided). If the one-sided p-value is less than 5% then the null hypothesis of no treatment effect is rejected.

A sample size of 30 subjects provides $\geq 90\%$ power for the primary endpoint assuming a mean percent reduction in ALP of 15% and a standard deviation of 25%. Power calculations use a 5% one sided alpha and a t-test. Sample size calculation were performed in PASS.

At least 6 subjects will participate in a PK sub study.

2 STATISTICAL METHODS**2.1 Analysis Populations**

The following analysis populations will be defined for statistical analysis:

- Screened population - All subjects who sign the study informed consent.
- Intention-to-treat (ITT) population - All subjects that receive at least one dose of HTD1801. This population will be used for the primary endpoint, as well as all efficacy, safety, and baseline/demographic analyses and summaries.
- Per Protocol (PP) Population – All subjects in the ITT population who provide a Week 12 assessment and 80% study drug compliance. This population will be used for selected efficacy analyses and summaries.

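### SAP 1.5 keeps an unqualified one-sided 5% rejection rule although enrolment may end on favourable ALP results with no threshold, so 5% is not assured, and the rule conflicts with the descriptive status given elsewhere (modest effect)

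*SAP*

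**What the plan says.** **The decision rule.** SAP 1.5 sets a one-sided 5% level and states: "If the one-sided p-value is less than 5% then the null hypothesis of no treatment effect is rejected". The same level appears in the Protocol synopsis (1.1), Protocol 12.1 and SAP 2.5.

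**The look and the early close.** SAP 2.8: "Data will be summarized at study completion, as well as when 15 subjects have reached Week 12". That summary is descriptive and includes the primary endpoint. Enrolment may then end early "if prior to enrollment of 30 subjects, the results provide sufficient preliminary evidence of efficacy that warrant further evaluation in a placebo-controlled study". Protocol 12.4.7 allows the same "should the scientific goal (evaluate the effects of HTD1801 on serum ALP) of the study be achieved with the currently available data", without a look time. Neither section gives a numerical criterion.

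**Ending the study.** Protocol 13.2 concerns suspension or termination of the study, not enrolment. Its possible grounds include "Demonstration of efficacy that would warrant stopping" and "Determination that the primary endpoint has been met", neither of them defined.

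**Who decides.** Protocol 4.4: "The end of enrollment if less than 30 subjects will be a collaborative decision between regulatory and Sponsor entities". This names the parties, not the result that would justify the decision.

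**Status of the test.** SAP 2.5 makes no multiplicity adjustment and calls the p-values descriptive. Protocol 12.4.2 places the tests closer to description than to confirmation and concedes that the true level may differ from 5%. The reason it gives is a small sample with possibly skewed data; it does not mention the interim look.

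**Who is analysed.** SAP 2.1 defines ITT as "All subjects that receive at least one dose of HTD1801. This population will be used for the primary endpoint". SAP 2.5.1.1 restricts the estimand to subjects on treatment with Week 12 data. Protocol 4.4 ends the study at the last subject's last visit.

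**The concern.** If a favourable result at 15 subjects can close enrolment, and an unfavourable one lets the study run on to 30, the final sample size depends on the data being tested. An unadjusted 5% test applied afterwards no longer has a 5% error rate in general. No formal interim test is needed for this; a descriptive summary is enough if it drives the decision. How far the error moves depends on a trigger that is not written down.

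There is also a conflict of status. SAP 1.5 leads a report writer to say that the null was rejected. SAP 2.5 and Protocol 12.4.2 lead the same writer to say that the p-value only describes the data. What is at stake is how the main result of an uncontrolled study is worded when it is used to justify a placebo-controlled one, and whether its readers are told that an early close makes the estimate look better than it is.

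**Working it through.** **1. Inputs.** From SAP 1.5: mean reduction 15%, SD 25%, N = 30, one-sample t-test, one-sided 0.05. From SAP 2.8: one look at 15 subjects. The documents give neither the trigger *c* (an interim p-value) nor the overrun *k* (subjects beyond the first 15 who are already enrolled at the close and later supply Week 12 data). Both are assumptions here and are varied. Data are taken as normal.

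**2. The plan's own figure.** Standardised effect 15/25 = 0.6; noncentrality 0.6 × √30 = 3.286; critical t on 29 df = 1.699; power = 94.1%. The stated 90% or more is reproduced. The smallest N that gives 90% is 26.

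**3. Why overrun counts.** The definitions in Protocol 4.4, SAP 2.1 and SAP 2.5.1.1, read together, put subjects already enrolled at an early close into the final test. No sentence says so directly.

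**4. Type I error.** If p at n = 15 is below *c*, the final test uses 15 + *k* subjects; otherwise it uses 30. Then

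error = P(stop and reject at 15 + *k*) + P(no stop and reject at 30).

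For *c* = 0.05 and *k* = 0, every stopped null trial rejects, so the first term is 5.0%. The second is 3.1%, total 8.1%. Simulation of at least 1 million null trials per cell gives:

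| Assumed trigger at 15 | k = 0 | k = 3 | k = 5 | k = 10 | k = 15 (N = 30) |
|---|---|---|---|---|---|
| p<0.10 | 7.1% | 6.6% | 6.1% | 5.4% | 5.0% |
| p<0.05 | 8.1% | 6.3% | 5.9% | 5.3% | 5.0% |
| p<0.01 | 5.4% | 5.3% | 5.3% | 5.1% | 5.0% |
| p<0.001 | 5.0% | 5.0% | 5.0% | 5.0% | 5.0% |

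**5. Power and interval at a true 15% reduction, trigger p<0.05, k = 3 / 5 / 10.** Power is 92.4 / 92.7 / 93.5%, still above 90%. Coverage of the 95% confidence interval is 95.3 / 95.2 / 95.1%; under no effect it is 94.1 / 94.4 / 94.8%.

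**6. Estimate at a true 15% reduction.**

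| | k = 3 | k = 5 | k = 10 |
|---|---|---|---|
| All trials, trigger p<0.05 | 15.7% | 15.5% | 15.2% |
| Stopped trials, trigger p<0.05 | 17.4% | 17.2% | 16.7% |
| Stopped trials, trigger p<0.001 | 22.3% | 21.6% | 20.3% |

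Much of the excess in stopped trials is selection. Trials with p<0.05 at 15 that are nevertheless run to 30 average 16.5%.

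**7. Chance of an early close at the planned effect.** 71% with p<0.05, 41% with p<0.01, 13% with p<0.001.

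**8. A formal alternative.** O'Brien-Fleming-type one-sided levels of about 0.009 at 15 and 0.047 at the end give an overall error of 5.1% with no overrun and 5.0 / 4.9 / 4.8% with 3 / 5 / 10. Power is about 94% with 30 evaluable subjects, and the chance of closing early at the planned effect is about 39%.

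**The case against.** The strongest reply is that the documents have already stepped back from a confirmatory claim. SAP 2.5 calls the p-values descriptive, Protocol 12.4.2 concedes that the level may not hold, the interim summary is itself descriptive, and closing below 30 is a joint decision with regulatory entities. If that reading governs, little depends on the exact level. With a few overrun subjects the excess is also small, and both of its drivers are assumed.

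This stands as a limit on the consequence. It does not remove the point. SAP 1.5 carries its rejection sentence with no qualification, in a section titled as the decision rule. The caveat in Protocol 12.4.2 rests on skew and sample size, and the remark on multiplicity in SAP 2.5 does not mention the look.

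A reader might also infer more than the documents support:

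- **An error of 10% or more.** Looks at 15, 20, 25 and 30, stopping at the first p<0.05, would give 10.0%; a look after every subject from 15 to 30 would give 12.4%. Protocol 12.4.7 sets no look time, but SAP 2.8 plans one interim summary and nothing describes repeated testing.
- **A faulty sample size.** The power statement at a fixed 30 is correct.
- **Protocol 13.2 as an enrolment rule.** It lists circumstances that may justify suspending or terminating the study, and does not mention enrolment.
- **A trial-wide bias of several points.** Averaged over all trials, the estimate is less than 1 point too high with 3 or more overrun subjects. The larger figures belong to trials that stopped.

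**Conclusion.** The point holds in a limited form. The 5% level is stated as a property of the design, but the design does not secure it, because favourable ALP results can end enrolment on an unwritten criterion before an unadjusted test. Separately, the rejection rule in SAP 1.5 contradicts the descriptive status in SAP 2.5 and Protocol 12.4.2.

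The size is modest and conditional: about 5.3 to 6.3% with one look at 15, a p<0.05 trigger and 3 to 10 overrun subjects. The 8.1% figure requires that no overrun subject contributes. A strict trigger, or a sample that still reaches 30, brings the error back to 5.0%. Certainty is high that the threshold is missing and the wording conflicts. The exact size is less certain, since it rests on the assumed trigger, overrun and normal data. This should be corrected, but it does not undermine the study.

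**What to change.** **Preferred: make the descriptive status consistent.**

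1. In SAP 1.5, replace the rejection sentence with:

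> The one-sided p-value is descriptive; no accept/reject conclusion is drawn, and the 5% level is used for sample-size planning only because enrolment may be stopped on interim ALP results.

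2. Make the same change where the Protocol synopsis (1.1), Protocol 12.1 and SAP 2.5 say that testing is at a 5% level. Deleting the SAP 1.5 sentence alone would leave those statements standing.
3. Point the two efficacy items in Protocol 13.2 to SAP 2.8.
4. State in SAP 2.8 that the final estimate and 95% confidence interval use all enrolled subjects with on-treatment Week 12 data, including those enrolled before an early close.
5. Add that, if enrolment closes early, the report gives the basis for stopping and says that the estimate from a trial stopped for a favourable result tends to overstate the effect. It should not call that bias modest: the stopped-trial averages above run from about 17% to 22% against a true 15%.

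**Alternative: keep a formal 5% test.** Prespecify an interim boundary and a matching final level, for example about 0.009 at 15 and 0.047 at the end, and remove the descriptive wording for that test. The choice of boundary is the sponsor's. A very strict cut such as 0.001 also holds the level, but reduces the chance of closing at 15 to about 13% at the planned effect.

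**Cost.** A few lines in each document, with no change to sample size, visits or data. The preferred route gives up the formal decision rule, which Protocol 12.4.2 already discounts. The alternative makes early closure less likely than a p<0.05 trigger would (about 39% against 71%).
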